10.2 Visit 1a (Screening Visit – Day -3 to Day 1)

At the Screening Visit, the patient's eligibility for study participation will be determined by checking all inclusion and exclusion criteria as specified in Section 8.

Medical history will be recorded at the Screening Visit. Investigators should document the occurrence, signs, and symptoms of all prior significant illnesses. Medical conditions ongoing at the time when informed consent is given or at the Screening Visit (Visit 1a) are to be regarded as concomitant. Medical history will include alcohol consumption and smoking history, if applicable.

Illnesses first occurring or detected during the study and/or worsening of a concomitant illness during the study are to be documented as AEs on the eCRF in accordance with Section 12.7. All changes not present at the Screening Visit or described in the past medical history and identified as clinically noteworthy must be recorded as AEs.

Additionally, demographic data will be collected for all patients and include year of birth, sex, ethnic origin (race) and iris colour.

The Screening Visit (Visit 1a) will entail the following evaluations:

- Inclusion/exclusion criteria
- Medical history
- Demographics
- Concomitant medications
- Recording of (S)AEs
- Measurement of vital signs (blood pressure and heart rate)
- Physical examination
- Measure height and weight
- Review of concomitant medications
- BCDVA both eyes
- Slit lamp examination **both eyes**

- Corneal photo without fluorescein both eyes
- Fluorescein stain test and corneal photo- both eyes
- Corneal sensitivity **both eyes**
- Fundus examination **both eyes**
- Schirmer test without anaesthesia
- Urine pregnancy test (for females of childbearing potential)

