15.3.2 Analysis of Secondary Efficacy Endpoints

Categorical secondary endpoints will be analysed using the same analysis used for the primary endpoint.

The analysis of continuous endpoints will be based on an analysis of covariance (ANCOVA) with treatment and site as main effects and baseline value and disease stage as covariates.

Time to event endpoints will be evaluated by means of Kaplan-Meier survival analysis using log-rank test. The Cox's proportional hazard model will be used in order to manage covariates in the proper way.

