4.3. Determination of Sample Size

A total of 108 patients will be randomly assigned to 1 of the 3 active treatment arms or the vehicle treatment arm (27 patients per arm). Randomisation will be stratified by disease stage (Stage 2, Stage 3) and region (Europe, North America).

Considering an estimated response rate of 27% for the vehicle treatment arm based on studies conducted in a similar patient population with cenegermin (Oxervate) and with approximately 80% of power and a 2-sided alpha of 0.05, the sample size of 27 patients per group (including a 15% estimate of dropout rate) should allow analysis to show a difference of at least 45% between the active treatment arms and the vehicle treatment arm.

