5.3. Secondary Efficacy Endpoints

- Percentage of patients who achieve a 5-, 10-, and 15-letter mean improvement in BCDVA by the ETDRS chart at Week 8 compared to baseline (in all patients and in patients with a central location of the PED or corneal ulcer, respectively).
- Percentage of patients achieving complete corneal healing of PED or corneal ulcer at Week 8, defined as no corneal fluorescein staining in the area of the PED or corneal ulcer as assessed by the investigator.
- Time to complete corneal healing of PED or corneal ulcer defined as no corneal fluorescein staining in the area of the PED or corneal ulcer as assessed by an independent central reading.
- Time to complete corneal healing of PED or corneal ulcer defined as no corneal fluorescein staining in the area of the PED or corneal ulcer as assessed by the investigator.
- Percentage of patients having deterioration of the disease at Week 8 (defined as increase in lesion size ≥ 1 mm compared to baseline as assessed by the investigator, or mean decrease in BCDVA by > 5 letters compared to baseline, or progression in lesion depth to corneal melting or perforation, or onset of infection).
- Mean change in BCDVA from baseline to Week 8 in all patients and in patients with a central location of the PED or corneal ulcer, respectively.
- Percentage of patients with improvement in corneal sensitivity from baseline as measured by Cochet-Bonnet aesthesiometer at Week 8.

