9.7. Treatment Compliance

Patients will be instructed to bring their unused/partially used/empty containers back for inspection at each study visit, and the number of opened BFS containers will be recorded. Patients will also be instructed to fill out a paper diary recording the date and time of study drug administration, which should be brought to the site at each study visit and reviewed with the patient. Patient compliance with the treatment will be assessed overall.

Overall compliance will be assessed by number of opened BFS containers. Noncompliance is defined as taking less than 80% or more than 120% of study drug during any outpatient evaluation period. Discontinuation of treatment for noncompliance is at the investigator's discretion and is to be noted on the eCRF.

Overall compliance (%) = (Number of used BFS containers) / [4 * (number of BFS to be used based on actual number of days of treatment)] * 100

With actual number of days of treatment calculated as:

Actual number of days = (last treatment administration date) - (first treatment administration date) + 1

Overall compliance will be summarised in a table by treatment group and overall based on the SAF population, and all data will be presented in a by-patient listing.

10. Efficacy

The analysis of all efficacy endpoints will be performed for the mITT population. Tertiary sensitivity analyses of the primary efficacy endpoint will also be performed on the PP population. The vehicle group will be used as reference group for all statistical tests.

All categorical endpoints will be analysed using the Cochran-Mantel-Haenszel (CMH) test stratified by region at randomisation as well as NK stage at randomisation. SAS procedure proc freq will be used.

All time-to-event endpoints will be evaluated by means of Kaplan-Meier (Kaplan & Meier 1958) survival analysis using a log-rank test. The Cox's proportional hazard model is used to estimate the hazard ratios, 95% confidence limits and p-values and includes covariates such as treatment group and randomisation strata, i.e. NK stage and region. SAS procedure proc lifetest will be used for the Kaplan-Meier analysis and proc phreg will be used for the Cox model.

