10.3. Secondary Efficacy Endpoints and Analyses

If significance is reached for the three doses on the primary endpoint, the gate keeping procedure used for the primary endpoint will also be used for secondary endpoints (in the hierarchical order as listed in section 5).

10.3.1. Secondary Efficacy Endpoint 1

The percentage of patients who achieve a \geq 5-, 10-, and 15-letter mean improvement in BCDVA by the ETDRS chart at Week 8 compared to baseline will be summarised for all patients and for patients with a central location of the PED or corneal ulcer.

The analysis will be performed on the mITT population according to the estimand framework and ICE definitions of the binary secondary efficacy endpoints (Section 7.2) using the CMH test controlling for randomisation strata at Week 8. Missing data will be imputed with single value imputation as per Section 8.3.2. A similar table output as for the primary efficacy analysis will be provided by all patients and by only patients with a central location of PED or corneal ulcer.

A descriptive frequency table will present the number and percentage of patients per visit and overall that have reported finger counting, hand motion, light perception or no light perception based on observed data.

10.3.2. Secondary Efficacy Endpoint 2

The percentage of patients achieving complete corneal healing of PED or corneal ulcer at Week 8, defined as no corneal fluorescein staining in the area of the PED or corneal ulcer as assessed by the investigator, will be summarised. The analysis will be performed on the mITT population according to the estimand framework and ICE definitions of the binary secondary efficacy endpoint (Section 7.2) using the CMH test controlling for randomisation strata at Week 8. Missing data will be imputed with single value imputation as per Section 8.3.2. The same table output as for the primary efficacy analysis will be created.

10.3.3. Secondary Efficacy Endpoint 3

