Note: Deterioration of the disease at Week 8 is defined as 1) increase in lesion size by \geq 1mm as assessed by the investigator compared to baseline or 2) mean decrease in BCDVA by \geq 5 letters compared to baseline or 3) progression in lesion depth to corneal melting, perforation or onset of infection.

This document is confidential.

SAP Version: 1.0, 31-May-2024

Controlled Document ID: 3903A.02, Effective Date 31-Aug-2020

Sponsor: Recordati Rare Diseases; Protocol No.: REC0559-B-001

Table 14.2.2.6.1 Mean Change in BCDVA from Baseline to Week 8 - Secondary Efficacy Endpoint 6 (mITT)

Location: <location>

	REC 0/0559 0.5 μg/day (N=xx)	REC 0/0559 2.5 μg/day (N=xx)	REC 0/0559 5.0 μg/day (N=xx)	Vehicle (N=xx)
Intercurrent events (ICE) up to Week 8, n (%)				
ICE1: Treatment discontinuation due to treatment-related AE	n (xx)	n (xx)	n (xx)	n (xx)
ICE2: Treatment discontinuation due to other reasons	n (xx)	n (xx)	n (xx)	n (xx)
ICE3: Start of rescue treatments/procedures	n (xx)	n (xx)	n (xx)	n (xx)
ICE4: Treatment discontinuation due to death	n (xx)	n (xx)	n (xx)	n (xx)
Mean change in BCDVA from baseline to week 8				
n	X	x	X	X
Mean (SE)	xx.x (x.xx)	xx.x (x.xx)	xx.x (x.xx)	xx.x (x.xx)
Minimum	XX	XX	XX	XX
Maximum	XX	XX	XX	XX
LSM estimate	x.xx	x.xx	x.xx	x.xx
95% confidence interval	(x.xx, x.xx)	(x.xx, x.xx)	(x.xx, x.xx)	(x.xx, x.xx)
LSM difference	x.xx	x.xx	x.xx	
95% confidence interval	(x.xx, x.xx)	(x.xx, x.xx)	(x.xx, x.xx)	
p-value [1]	x.xxx	X.XXX	X.XXX	

n: Number of patients with data available, N: Number of patients within treatment group, SE: Standard Error, BCDVA: Best Corrected Distance Visual Acuity, LSM: Least Squares Mean

Note: The LSM estimates, LSM differences and 95% confidence intervals as well as the p-values are obtained from an ANCOVA with treatment as main effect and baseline value (last available value before treatment start) and randomisation strata disease stage and region as covariates.

Note: Multiple imputation (MI) with a Markov Chain Monte Carlo (MCMC) approach is used for any intermittent missing data. For monotone missingness up to Week 8 due to ICE1 and ICE3 assuming missing not at random (MNAR), MI is implemented with a control-based pattern approach (vehicle as reference). Observed data as collected will be used for ICE2 and MI under MAR assumption is used for any monotone missing data. Unobserved data due to ICE4 is imputed with a worst value single imputation approach.

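### The letter-gain endpoint is tested without baseline visual acuity as a covariate: a valid analysis that gives up a modest amount of precision

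*SAP*

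**What the plan says.** The first endpoint in SAP 5.3 is: "Percentage of patients who achieve a 5-, 10-, and 15-letter mean improvement in BCDVA by the ETDRS chart at Week 8 compared to baseline". SAP 10.3.1 analyses it under the "definitions of the binary secondary efficacy endpoints (Section 7.2) using the CMH test controlling for randomisation strata at Week 8". This applies the general rule at the start of SAP Section 10, "All categorical endpoints will be analysed using the Cochran-Mantel-Haenszel (CMH) test stratified by region at randomisation as well as NK stage at randomisation", and agrees with Protocol 15.3.2: "Categorical secondary endpoints will be analysed using the same analysis used for the primary endpoint". Visual acuity is not a stratum. SAP 4.3 states: "Randomisation will be stratified by disease stage (Stage 2, Stage 3) and region (Europe, North America".

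Baseline acuity is available, since Protocol 10.2 lists "BCDVA both eyes" at Visit 1a. It is used when the same measurement is analysed as mean change (Secondary Endpoint 6). SAP 10.3.6 does not name the ANCOVA covariates, but the shell for Table 14.2.2.6.1 does: "ANCOVA with treatment as main effect and baseline value (last available value before treatment start", together with disease stage and region. Protocol 15.3.2 likewise specifies "treatment and site as main effects and baseline value and disease stage as covariates" for continuous endpoints.

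Neither the SAP text nor the shells contain a baseline-adjusted analysis of letter gain.

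**The concern.** Subtracting the baseline score to form a gain does not remove the dependence of the gain on that score. Entry requires 75 letters or fewer, with no lower letter limit, and SAP 10.3.1 plans a table for eyes graded below the chart, so a wide spread is foreseen. An eye entering at 75 must reach 90 for a 15-letter gain; an eye entering at 30 must reach 45.

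The plan treats baseline as worth adjusting for when the change is analysed as a mean, then leaves it out once the change is dichotomised, and gives no reason. With 27 patients per arm, a chance difference in starting vision passes into the responder difference, and variation that baseline could explain stays as noise. All three dose comparisons share one vehicle arm, so an imbalance in that arm pushes all three the same way.

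**Working it through.** **The plan's own figure.** No power is stated for letter gain. The 27 per arm comes from the primary endpoint: 27% against 72%, two-sided 0.05, about 80% power, 15% dropout. The normal formula with continuity correction gives 23 evaluable per arm, and 23/0.85 = 27.06. Exact Fisher power is 79.4% at 22 and 82.8% at 23 per arm. The figure reproduces.

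**Assumptions, none of them in the documents.** Baseline is normal with mean 42 and SD 22, truncated to 0–75; residual SD is 15 letters; true benefit is 12 letters. The slope of gain on baseline is −0.2, −0.35 or −0.5 letters per letter.

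**Chance imbalance.**
- The SD of the difference in arm means, in baseline SD units, is √(2/27) = 0.272. It exceeds 0.25 SD in 36% of trials and 0.5 SD in 6.6%.
- Truncation reduces the baseline SD from 22 to 17.7, so one SD of imbalance is 17.7 × 0.272 = 4.8 letters. The untruncated SD would give 6.0, which overstates it.
- At slope −0.35 the shift in mean gain is 0.35 × 4.8 = 1.7 letters. The SD of gain is √(15² + (0.35 × 17.7)²) = 16.2. The peak normal density is 0.40, so the responder difference moves by at most about 0.40 × 1.7/16.2 = 4 points. Simulation also gave about 4 points, and about 5 at slope −0.5.

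**Power.** The planned CMH was compared with the same stratified test applied to residuals after regression on baseline and strata, with 27 per arm, 4,000 trials per cell, and cuts at 10 and 15 letters:

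| Slope | CMH | Adjusted for baseline |
|---|---|---|
| −0.2 | 57–58% | 57–58% |
| −0.35 | 54–55% | 56–57% |
| −0.5 | 48–49% | 55–56% |

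A repeat at the 10-letter cut gave gains of about 0, 3 and 7 points. Null rejection across these runs was 4.2–5.6%.

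**Composite failures.** SAP 7.1 and 7.2 count related-AE discontinuation, rescue and death as failures whatever the letter score, which weakens the link with baseline. With an assumed 15% of such failures the gains fall to about 0, 2 and 3 points. With 25% they run from −0.3 to 3 points.

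**Cross-check with a different model.** A latent-gain model took the 27% vehicle rate as an assumption and gave gain a correlation r with baseline. It compared logistic score tests with and without baseline. Baseline added 0 points at r = 0, about 2–3 at 0.3 and 3–7 at 0.5. The steepest slope above implies r = 0.5 × 17.7/√(15² + (0.5 × 17.7)²) = 0.51, so the two models agree. At r = 0.7, beyond that slope range, the gain was 6–16 points. CMH type I error was 4.4–5.1%; the logistic score tests ran at 5.3–6.0%.

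**The case against.** The strongest reply is that nothing is broken. The CMH test is valid and prespecified, and the SAP follows the protocol's rule for categorical endpoints. The same measurement is tested with baseline adjustment in Endpoint 6, and baseline BCDVA by arm appears in Table 14.2.2.6.2, so an imbalance would be visible. The gain from adjustment rests on assumed inputs and is nil at a shallow slope. All of this stands and limits the size of the point. It does not explain why a baseline already collected, and already used for the mean change, should be left out here.

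Three stronger readings are tempting and are not supported:
- A reader might infer that omitting baseline inflates false positives. Every check kept the CMH near 5%.
- A reader might infer that adjustment would bring Endpoints 1 and 6 into agreement. SAP 7.2 handles intercurrent events differently for the two (composite failure and LOCF for the binary endpoint; control-based or MAR multiple imputation, with worst value for death, for the continuous one), so they can still differ.
- A reader might infer that a leading confirmatory test is compromised. Under SAP 10.3, secondary testing opens only if all three doses are significant on the primary endpoint, and in the Section 5 order the key secondary endpoint comes before this one.

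**Conclusion.** The point holds as a modest matter of precision and chance imbalance. Under the stated assumptions the adjusted test held its size. It gained about 0–7 points of power over slopes −0.2 to −0.5, or about 0–3 with 15% composite failures. A one-SD baseline imbalance of 4.8 letters moves the responder difference by about 4 points at slope −0.35. If gain is nearly unrelated to baseline, nothing is gained. The effect on formal conclusions is remote, but the estimates can still inform dose selection, which is a primary objective, and for that a chance shift in the vehicle arm matters.

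**What to change.** Before unmasking, amend SAP 10.3.1 as follows:
- Adjust the letter-gain comparison for baseline BCDVA as a continuous covariate, together with NK stage and region.
- Report a standardised risk difference with confidence interval from a penalised or small-sample logistic model. Alternatively, take the p-value from the residual-based stratified test and pair it with a baseline-adjusted risk difference; the residual test alone supplies no effect estimate to replace those in the shell.
- State that eyes reading no letters enter with a baseline score of 0, with an off-chart indicator if needed.
- Keep the planned CMH table as supportive.

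The calculations support baseline BCDVA only. A further covariate such as lesion location was not examined and is not proposed.

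The cost is SAP wording, a revised shell and slightly more analysis work; no new data are needed. A plain logistic score test runs at about 6% at this sample size and should not be used uncorrected.

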8 SELECTION OF STUDY POPULATION

8.1 Inclusion Criteria

Individuals must meet all of the following criteria to be included in the study:

- 1. Have read, understood, and signed the ICF.
- 2. Be a male or female aged \geq 18 years at the time of ICF signature.
- 3. Have Stage 2 moderate (PED) or Stage 3 severe (corneal ulcer) NK involving only 1 eye (study eye) and of at least 2 weeks duration. Patients with Stage 1 NK in the fellow eye can be enrolled.
- For the study eye:
- 4. Have no objective clinical evidence of improvement in the PED or corneal ulceration within the 2 weeks before the Screening Visit despite use of conventional non-surgical treatment (eg, nonpreserved ocular lubricants, nonpreserved topical antibiotics, oral doxycycline, patching, serum tears, and/or therapeutic contact lenses) as determined by the investigator's or referring physician's medical record.
- 5. Have decreased corneal sensitivity (≤ 4 cm using the Cochet-Bonnet aesthesiometer) within the area of the PED or corneal ulcer and outside of the area of the defect in at least one corneal quadrant.
- 6. Have a BCDVA score \leq 75 ETDRS letters in the study eye, due to NK.

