11.3 BCDVA Examination

Assessment of BCDVA for the study eye and the fellow eye will be done using the ETDRS protocol.²⁰ Distance visual acuity will be measured with best correction. Qualified study personnel following manifest refraction and using certified visual acuity equipment/lanes will perform the assessment. The BCDVA should precede any examination requiring contact with the study eye. The method of visual acuity assessment should remain consistent throughout a patient's study participation.

The BCDVA examination will start from the distance of 4 meters from the chart. The number of letters correctly read by the patient will be collected. Eyes reading 19 or fewer letters correctly at 4 meters should be tested at a 1 meter distance. If visual acuity is so poor that the patient cannot read any letter from 1 meter then counting fingers, hand motion test, and light perception should be tested.

A detailed description of the ETDRS BCDVA procedure will be provided to sites in form of an accompanying manual.

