date at (V8/D56) if available. In case the patient has no efficacy assessment done at (V8/D56), the censoring time (days) after the ICE occurrence will be set to Day 56 which is the last scheduled efficacy assessment day in the 8 week treatment administration period as planned per protocol. The analysis will be performed on the mITT population according to the estimand framework and ICE definitions for the time to event endpoints (Section 7.2). Missing data will be imputed with single value imputation as per Section 8.3.2..

The HRs and their 95% Wald CIs and p-values, as well as the estimate and 95% CI for the median, 25% and 75% quartiles of time to complete corneal healing, will be reported in a table; the survival probability for the treatment groups will be plotted in a figure.

10.3.5. Secondary Efficacy Endpoint 5

Deterioration of the disease at Week 8 is defined as an increase in lesion size ≥ 1 mm compared to baseline as assessed by the investigator, or mean decrease in BCDVA by > 5 letters compared to baseline, or progression in lesion depth to corneal melting or perforation, or onset of infection.

The analysis will be performed on the mITT population according to the estimand framework ind ICE definitions of the binary secondary efficacy endpoint (Section 7.2) using the CMH test controlling for randomisation strata at Week 8. Missing data will be imputed with single imputation as per Section 8.3.2. The same table output as for the primary efficacy analysis will be created.

10.3.6. Secondary Efficacy Endpoint 6

An ANCOVA will be performed for the mean change in BCDVA from baseline to Week 8 in all patients and in patients with a central location of the PED or corneal ulcer with missing values imputed as per estimand strategies and definitions of intercurrent events for continuous secondary efficacy endpoints as described in Section 7.2. Missing data will be imputed with MI as per Section 8.3.2. The least squares mean (LSM) estimates and 95% CIs of each treatment group as well as the LSM differences, 95% CIs, and p-values from the comparison between the REC 0/0559 groups and vehicle group will be reported separately for all patients and for patients with a central location of PED or corneal ulcer. Descriptive summary of the mean change from baseline at Week 8 based on imputed data will also be presented. In addition, BCDVA values and changes from baseline are summarised descriptively by visit based on observed data only.

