95% Confidence Interval	(x.xx, x.xx)	(x.xx, x.xx)	(x.xx, x.xx)	
Cochran-Mantel-Haenszel (CMH) Test				
Value	x.xx	x.xx	x.xx	

This document is confidential.

SAP Version: 1.0, 31-May-2024 Controlled Document ID: **3903A.02**, Effective Date 31-Aug-2020 Filing requirements: TMF

Sponsor: Recordati Rare Diseases; Protocol No.: REC0559-B-001

	REC 0/0559	REC 0/0559	REC 0/0559	
	0.5 μg/day	$2.5 \mu g/day$	5.0 µg/day	Vehicle
	(N=xx)	(N=xx)	(N=xx)	(N=xx)
p-value [1]	X.XXX	X.XXX	X.XXX	

n: Number of patients with data available, N: Number of patients within treatment group, NA: North America, EU: Europe, AE: Adverse

Note: Percentage is based on number of patients within treatment group.

Note: Deterioration of the disease at Week 8 is defined as 1) increase in lesion size by >= 1mm as assessed by the investigator compared to baseline or 2) mean decrease in BCDVA by >= 5 letters compared to baseline or 3) progression in lesion depth to corneal melting, perforation or onset of infection.

Note: Occurrence of ICE1, ICE3 and ICE4 are considered as failure at Week 8. Observed data as collected are used for ICE2 and monotone missing values are imputed using last observation carried forward (LOCF) up to Week 8.

- [1]: Vehicle group is used as reference for the risk differences, OR and CMH test. For the confirmatory analysis based on the primary estimand a gate keeping procedure is applied in the following order:
- 1. REC 0/0559 5.0 μ g/day vs vehicle at 0.04 alpha level and if significant, REC 0/0559 2.5 μ g/day vs vehicle at 0.05 alpha level. If both tests are significant, REC 0/0559 0.5 μ g/day vs vehicle is tested at 0.05 alpha level.
- 2. REC 0/0559 2.5 μ g/day vs vehicle at 0.01 alpha level and if significant, REC 0/0559 5.0 μ g/day vs vehicle at 0.05 alpha level. If both tests are significant, REC 0/0559 0.5 μ g/day vs vehicle is tested at 0.05 alpha level.

Programming Note:

See section 15 for Format of output in the SAP. Present footnotes on first page if needed.

This document is confidential.

SAP Version: 1.0. 31-May-2024

Controlled Document ID: 3903A.02, Effective Date 31-Aug-2020

Sponsor: Recordati Rare Diseases; Protocol No.: REC0559-B-001

Table 14.2.2.5.2 Frequency Summary of Patients Having Deterioration of the Disease at Week 8 - Secondary Efficacy Endpoint 5 (mITT)

Programming Note:

The layout is the same as Table 14.2.2.1.3 but replace 'improved' with 'deterioration' and replace with following footnotes:

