See section 15 for Format of output in the SAP. Sort listing by treatment group (lowest REC 0/0559 to highest and then Vehicle) and patient ID, eye (display first study eye then fellow eye), visit, start date and test and assessments as ordered on the CRF. Add derived endpoints for Reduction of greatest diameter at the end of Fluorescein Test results for each visit. If a patient is not treated or a screen failure display 'Not Treated' or 'Screen Failure' in first column as Treatment group and sort these patients at the end of the listing. If multiple slit lamp results for the cornea separate by comma in the Results column.

This document is confidential.

SAP Version: 1.0. 31-May-2024

Controlled Document ID: 3903A.02, Effective Date 31-Aug-2020

Sponsor: Recordati Rare Diseases; Protocol No.: REC0559-B-001

Listing 16.2.6.3 Best Corrected Distance Visual Acuity (BCDVA) (Enrolled Set)

Patient ID/ Treatment group/ Region/ Disease stage \$/ Study eye	Eye	Visit	Date of Assessment (Study Day)	Assessment	Result
Xxxxx/ REC 0/0559 0.5 µg/day/ NA/ 2/ Right	Study	Visit x	Ddmmmyyyy (xx)	ETDRS Letter Score (4m)	xxx
-				ETDRS Letter Score (1m)	xx
				Total ETDRS Letter Score (derived)	xxxx
				Difference of Total ETDRS Letter Score to Visit 1a (derived)	XXX
				If zero (0) letters read correctly at 1m indicate best visual acuity	Hand motion
		Visit y	Ddmmmyyyy (xx)	ETDRS Letter Score (4m)	xxx
				Total ETDRS Letter Score (derived)	xxxx
				Difference of Total ETDRS Letter Score to Visit 1a (derived)	xxx
	Fellow	Visit x	Ddmmmyyyy (xx)	ETDRS Letter Score (4m)	xxx
			- 1111		
Xxxxx/ yyyy/ zz/ v/ uuuuuu	Study	Visit x	Ddmmmyyyy (xx)	ETDRS Letter Score (4m)	xxx
, ,				Total ETDRS Letter Score (derived)	XXXX

ETDRS: Early Treatment Diabetic Retinopathy Study

\$: Stage 2 = Moderate, Stage 3 = Severe

Note: - = unknown or not evaluated, N/A = not applicable, NA = North America, EU = Europe

Analysis dataset: ADxx.SAS7BDAT;

Programming Note:

See section 15 for Format of output in the SAP. Sort listing by treatment group (lowest REC 0/0559 to highest and then Vehicle) and patient ID, eye (study eye first, then fellow eye), visit, start date and Assessment as ordered on the CRF. If a patient is not treated or a screen failure display 'Not Treated' or 'Screen Failure' in first column as Treatment group and sort these patients at the end of the listing.

This document is confidential.

SAP Version: 1.0, 31-May-2024

Controlled Document ID: 3903A.02, Effective Date 31-Aug-2020

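### Eyes reading 0–5 letters at baseline cannot meet the vision component of the deterioration endpoint, so isolated visual loss in them is not counted

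*SAP*

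**What the plan says.** SAP 10.3.5, in line with SAP 5.3 and Protocol 6.2.2, classes a patient as deteriorated at Week 8 if any one of several things has happened: the lesion has grown by at least 1 mm, vision has fallen, the lesion has deepened to melting or perforation, or infection has begun. The vision criterion is "or mean decrease in BCDVA by > 5 letters compared to baseline". The footnotes of shells 14.2.2.5.1 and 14.2.2.5.2 set a different threshold, "mean decrease in BCDVA by >= 5 letters compared to baseline".

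BCDVA is a letter count. Protocol 11.3 says: "The number of letters correctly read by the patient will be collected". For off-chart eyes it adds that if the patient "cannot read any letter from 1 meter then counting fingers, hand motion test, and light perception should be tested". Listing 16.2.6.3 follows the same logic, with a line headed "If zero (0) letters read correctly at 1m indicate best visual acuity". The same listing derives change only by comparing total letter scores with Visit 1a.

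The off-chart categories are used in one analysis, the descriptive table in SAP 10.3.1 of patients who "have reported finger counting, hand motion, light perception or no light perception based on observed data". Its shell, Table 14.2.2.1.2, has rows for these categories at baseline as well as at later visits.

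Entry criterion 6 in Protocol 8.1 allows at most 75 "ETDRS letters in the study eye, due to NK" and sets no minimum. Exclusion 13 in Protocol 8.2 removes severely impaired eyes only where the investigator sees no potential for improvement.

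SAP 7.2 applies the intercurrent-event rules of Table 3 to the binary secondary endpoints. The footnote of Table 14.2.2.5.1 accordingly treats discontinuation for a related adverse event, rescue, and death as failure.

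**The concern.** The criterion is a fixed number of letters on a scale that stops at zero. Eyes at or near the bottom have no room to fall by that number, and the information that could show further loss (the off-chart category) is collected but does not enter the endpoint. The plan expects such eyes: the protocol has a procedure for them and the SAP has a baseline row for them.

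Deterioration is the plan's only responder endpoint for worsening disease, and the trial is meant to select the dose with the best benefit-risk ratio (SAP 3.1). The scoring also runs one way only. An eye at 0 letters can become a 5-, 10- or 15-letter improver under Secondary Efficacy Endpoint 1, but can never be recorded as having lost vision under Endpoint 5.

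**Working it through.** The plan gives no expected deterioration rate and no distribution of baseline acuity, so there is no stated figure to reproduce for this endpoint. The check is of the definition itself.

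**Inputs**
- Threshold: loss > 5 letters (SAP 10.3.5, SAP 5.3, Protocol 6.2.2), or >= 5 letters (footnotes of Tables 14.2.2.5.1 and 14.2.2.5.2).
- Scale: letters read, with minimum 0 (Protocol 11.3). Off-chart eyes carry 0 letters plus a category (Listing 16.2.6.3).
- Baseline range: 0 to 75 letters (Protocol 8.1, criterion 6).
- Planned arm size: 27 (SAP 4.3).

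**Step 1: the floor.** With baseline score b, the largest possible loss is b − 0 = b.

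| Baseline b (letters) | Largest loss | Can meet > 5? | Can meet >= 5? |
|---|---|---|---|
| 0–4 | 0–4 | no | no |
| 5 | 5 | no | yes |
| 6 or more | 6 or more | yes | yes |

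The lowest baseline that can meet the criterion is 6 letters under the SAP text and 5 letters under the shell footnotes. The floor exists under both wordings; only its edge moves.

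**Step 2: off-chart change.** Counting fingers to no light perception is 0 − 0 = 0 letters. Every other step among the four categories is also 0.

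**Step 3: routes that remain.** An affected eye can still count through lesion growth of at least 1 mm, melting, perforation or infection. It can also count as a failure after rescue during the 8 weeks, discontinuation for a related adverse event, or death. What is lost is visual decline with none of these.

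**Step 4: possible size.** Let s be the share of eyes at or below the floor and w the proportion of them whose vision truly worsens. If no other route catches any of them, the understatement of an arm's rate is s × w. Neither input is in the documents. Assuming s = 10–30% and w = 20%:
- Eyes affected per arm: 0.10 × 27 = 2.7 to 0.30 × 27 = 8.1, about 3 to 8.
- Understatement: 0.10 × 0.20 = 0.02 to 0.30 × 0.20 = 0.06, or 2 to 6 percentage points.
- Patients: 0.02 × 27 = 0.5 to 0.06 × 27 = 1.6 per arm.

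These are maxima under the assumed inputs, because any overlap with the other routes reduces them. If s is near 0, so is the effect.

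**The case against.** A reader might infer that a fall from counting fingers to no light perception is classed as no deterioration. The documents do not support that. The endpoint is met by any one component, rescue is available for worsening disease (Protocol 9.6.2), and its use in the 8 weeks counts as failure. The fall adds nothing to the vision component, but the patient is missed only if nothing else occurs.

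A reader might also infer that worsening is invisible elsewhere in the plan. It is not. Mean BCDVA change is a separate secondary endpoint (SAP 10.3.6), although it has the same letter floor. The off-chart categories are tabulated by arm and visit and listed by patient. Adverse events include conditions present at screening that worsen (Protocol 12.7.1), and ocular events are tabulated by eye (SAP 12.1).

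Three further points are fair. Exclusion 13 removes some very poor eyes, so the share may be small. If share and worsening are equal across arms, the difference between arms is not biased. And secondary endpoints are tested formally only if all three doses succeed on the primary endpoint, then in listed order (SAP 10.3); this one comes fifth among the secondaries, after the key secondary.

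These points limit the weight of the problem. They do not remove the gap in the definition: isolated visual loss in eyes at the floor cannot be counted, and the plan does not say how off-chart change should be scored for this endpoint.

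**Conclusion.** The point holds in a limited form. Under the SAP text, eyes with a baseline of 0–5 letters (0–4 under the shell footnotes) cannot meet the vision component, and every step among the off-chart categories scores 0 letters. Isolated visual loss in these eyes is missed; loss accompanied by another component or a failure event is not.

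The size cannot be determined from the documents. The figure of at most 2–6 points per arm is illustrative and rests on an assumed 10–30% share and 20% worsening. It should not be read as an estimate, nor as evidence of bias between arms.

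The conclusion assumes that an eye reading nothing at 1 metre has a total score of 0 and that scores cannot be negative. Listing 16.2.6.3 supports this, but the rule for the derived total score is not given in the protocol or SAP. It also reads failure, for this endpoint, as being counted as deteriorated.

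The conflict between > 5 and >= 5 letters is a separate, certain inconsistency. It affects any eye that loses exactly 5 letters, whatever its baseline.

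**What to change.** In SAP 5.3, SAP 10.3.5 and shells 14.2.2.5.1 and 14.2.2.5.2, add a rule for eyes at the floor:
- Baseline of 0 letters: the BCDVA component is met by a fall to a lower category in the order counting fingers, hand motion, light perception, no light perception.
- Baseline of 1–5 letters: the component is met only by a fall below counting fingers, so that a loss of 1–5 letters alone does not count. Without this limit, a drop from 1 letter to counting fingers would count as deterioration while a 5-letter loss from 40 would not.

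Report the number of such eyes per arm. Reconcile > 5 with >= 5 letters between the SAP text and the shells; if >= 5 is kept, the second band becomes 1–4 letters. Because the definition also stands in Protocol 6.2.2, record the change in SAP 2.3, before unmasking.

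The cost is a short addition to the text and one derivation from data already collected. The downside is that one component becomes categorical for what is presumably a minority of eyes.
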